#### 8.1.3 Other study parameters

The following variables will be collected from the medical records:

- Date of first histological diagnosis
- Details about treatment
  - o Treatment start date
  - o Type of treatments, including medication doses
  - o Radiation dose

- Date of surgery
- Sequence of treatments
- Response to treatment
  - Progression, stable disease, regression based on imaging
  - Tumour sizes on imaging (magnetic resonance imaging, computed tomography or ultrasound)
  - Recurrence (based on imaging), recurrence based on pathology
  - Date of recurrence
  - Treatment type of recurrent tumour, date of treatment of recurrence

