## **2. OBJECTIVES**

Primary objective: To evaluate HRQoL problems in adult DTF patients, regardless of their disease stage or treatment course, using the DTF-QoL, the EORTC QLQ-C30, and the EQ-5D-5L questionnaires.

Secondary objectives:

1. To compare the level of HRQoL of DTF patients to that of the general population (age- and sex-matched), using the EORTC QLQ-C30 (version 3.0).
2. To identify DTF patients who are at risk for late effects and/or impaired HRQoL (risk factors), using the baseline questionnaire, the DTF-QoL (version 1.0), the EORTC QLQ-C30 (version 3.0), and the EQ-5D-5L (version 1.0).
3. To evaluate patient preferences regarding their health care for DTF, using the healthcare utility and decision making questionnaires (both version 1.0).

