### **10.3 Other study parameters**

Information extracted from medical files will be used as follows:

- Date of first histological diagnosis: this variable will be used to calculate age at diagnosis using date of birth and date of first histological diagnosis,
- Details about treatment
  - o Treatment start date: this variable will be used to calculate age at the start of treatment using date of birth and the date of the start of the treatment. Additionally this variable can be used to calculate the time between the diagnosis and the start of treatment.
  - o Type of treatments, including medication doses: this variable will be used as numbers with corresponding percentages
  - o Radiation dose: this variable will be used in case a patient received surgery. This variable will be used descriptively
  - o Date of surgery: this variable will be used to calculate the age at the time of surgery. Additionally this variable can be used to calculate the time between the diagnosis or the first treatment and surgery.
  - o Sequence of treatments will be used descriptively
- Response to treatment

- Progression, stable disease, regression based on imaging: these variables will be used in a descriptive manner
- Tumour sizes on imaging (magnetic resonance imaging, computed tomography or ultrasound): these variables will be used to calculate mean size with standard deviation or median with interquartile range. Additionally this variable can be used to evaluate treatment outcome.

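### For treatment given over time, the chart list takes a start date but no stop date, so among patients off such treatment late effects cannot be told from effects of recently ended treatment

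*Combined protocol and SAP*

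**What the plan says.** Section 2 states secondary objective 2 as "To identify DTF patients who are at risk for late effects and/or impaired HRQoL (risk factors"), to be met with the baseline questionnaire, the DTF-QoL, the EORTC QLQ-C30 and the EQ-5D-5L. The documents do not define a late effect.

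Section 8.1.3 lists what is taken from the medical records. The treatment items are "Treatment start date", "Type of treatments, including medication doses", radiation dose, "Date of surgery" and "Sequence of treatments". For recurrence it adds "Treatment type of recurrent tumour, date of treatment of recurrence", which is one date, not labelled as start or end.

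Section 10.3 uses the start date for age at start, and then: "Additionally this variable can be used to calculate the time between the diagnosis and the start of treatment". The surgery date is used for age at surgery and for the interval from diagnosis or first treatment to surgery. No listed use runs forward from treatment to the questionnaire.

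Appendix 1 says the baseline questionnaire asks about treatments received and current treatment. It describes no treatment dates and refers to section 8.1.3 for the chart details. Section 8.1.2 forms subgroups by primary treatment type, with none by current treatment, treatment length or time since treatment.

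**The concern.** On any usual reading, a late effect is placed in time relative to the end of treatment. A start date does that only when treatment starts and ends at practically the same time. That is true of an operation but not of a drug taken for months or years.

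The design offers no other way to recover the information. Patients complete the questionnaires once (section 8.3), so no second measurement shows whether a deficit fades. Section 4.2 admits diagnoses from January 1990 to October 2019, so time since treatment may run from none to almost 30 years. A systemic-treatment subgroup could then pool patients on treatment, recently off it and long off it. The baseline questionnaire can separate the first of these; nothing listed separates the other two.

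At stake is what can be said under objective 2. A temporary deficit in patients who stopped recently could be reported as lasting, and length of exposure, a natural candidate risk factor, could not be examined.

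**Working it through.** The plan states no figure on this point, so the check is whether time since the end of treatment and length of treatment follow from the listed fields.

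**Derivability by treatment type**

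| Treatment | Dates or items available | Time since end | Length |
|---|---|---|---|
| Surgery | Date of surgery | Yes | Not applicable |
| Local treatment such as cryoablation | Start date | Yes, if a single session (assumption) | Not applicable |
| Radiotherapy | Start date, dose | Approximate, if the course was short (assumption) | Not collected |
| Systemic therapy | Start date, type, dose, sequence | No | No |
| Never treated | None needed | Not applicable | Not applicable |

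For systemic therapy the partial substitutes fall short. Dose without duration does not give exposure time. The date of a later treatment gives at most a rough upper bound on when the earlier line ended, and only in patients who had a later line. Response and tumour size describe the tumour, not the exposure.

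**A hypothetical pair.** Two patients start the same drug at the same dose in January 2015 and answer in January 2020. One stopped in March 2015, after 2 months, and has been off treatment for 58 months. The other stopped in December 2019, after 59 months, and has been off for 1 month. Both report past and not current treatment, and their listed treatment fields can be identical.

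**How large could the mixing be?** The documents give no input for this, so every value here is an assumption. Take a deficit on a 0–100 scale of 15 points when treatment stops, falling to a lasting 5 points with a half-life of one year, so that the deficit at t years is 5 + 10·2^(−t). If time since stopping is spread evenly over 0 to T years, the pooled mean is

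5 + 10·(1 − 2^(−T)) / (T·ln 2).

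- T = 5: 5 + 10·0.96875/3.466 = 7.80, an excess of 2.80 over the lasting 5.
- T = 15: 5 + 10·0.99997/10.397 = 5.96, an excess of 0.96.
- T = 30: 5 + 10·1.000/20.794 = 5.48, an excess of 0.48.

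With the same curve, patients in their first year off treatment average 12.21 points and those 2 to 5 years off average 6.05. The pooled excess thus ranges from about 0.5 to 2.8 points according to the assumed window alone. It would change again with a different half-life or starting deficit.

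**Room for subgroup splits.** Section 4.4 expects about 100 respondents, and section 8.1.2 names four primary treatment types. If all were treated and evenly spread, which is favourable, each type would hold 100/4 = 25 patients, and a two-way split by time since treatment would leave 25/2 = 12.5 per cell. Real cells will be uneven and many smaller. This argues for a descriptive display or a continuous time variable rather than a fixed cut-off.

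**The case against.** The strongest reply is that no planned analysis fails. The study calls itself exploratory (section 1), objective 2 is secondary, and the objective is worded as late effects and/or impaired HRQoL; the summary's versions omit late effects altogether. Section 8.1.2 plans descriptive scores by subgroup, and section 10.3 uses most chart items descriptively. Nothing in the plan estimates a late effect, so there is no planned quantity to call biased. This stands, and it limits the weight of the point. It does not remove it: section 2 names late effects, and the fields needed to speak about them after systemic therapy are not collected.

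A second reply is that much of the timing is already available. That also stands. A reader might infer that time off treatment cannot be derived for any treatment, but the documents do not support this. Surgery is dated, a single-session local treatment is dated by its start, and the current-treatment item separates on from off. Section 1 says active surveillance is recommended first line for most patients, so some may have no treatment to date.

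A third reply is that the 21 baseline items are not reproduced, so a date question cannot be excluded. That is correct. Appendix 1 describes none, and the sponsor could settle the matter in one sentence.

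**Conclusion.** The point holds for treatments given over time: fully for systemic therapy, approximately for radiotherapy. For these, treatment length and time since the end of treatment cannot be derived from the listed data. Among patients now off such treatment, objective 2 cannot distinguish late effects from effects of recently ended treatment.

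The size of any distortion is unknown. The documents give neither the number of patients affected, nor the spread of time since stopping, nor any course of recovery. The 0.5 to 2.8 points shown above follow from assumed values. A reader might take them as a known overstatement of a planned estimate; they are not, since the plan contains no such estimate. Nor would later repair mean reopening every chart, as might be inferred: only those of patients given systemic therapy or radiotherapy. The gap still cannot be closed at analysis from the data as listed.

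This is a moderate point: an inexpensive addition to data collection that changes what a secondary, exploratory objective can conclude.

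**What to change.** - **Section 8.1.3:** for each systemic or radiotherapy line, add a field for treatment stop date, or ongoing.
- **Section 10.3:** derive treatment duration, and the time from the end of each treatment to questionnaire completion. For surgery, count from its date, which the plan already collects but does not use in this way.
- **Section 8.1.2:** describe scores in the treatment subgroups by current versus past treatment and by time since the end of that same treatment. Time since the last treatment would not match subgroups built on primary treatment. With about 100 respondents, show this descriptively or treat time as continuous.
- **Reporting:** say in one line what is meant by a late effect, and limit any such statement to patients off treatment, with their time since treatment reported.

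The cost is one field per treatment line in charts already being opened for type, dose and start date, plus two derived variables. The downside is slightly more extraction time and some imprecise dates in older records. If the field is not added, the consistent alternative is to remove late effects from objective 2.

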## **8.2 Randomisation, blinding and treatment allocation**

Not applicable, as this study is no intervention study.

## **8.3 Study procedures**

Selected patients will receive an invitation package by mail from their (former) treating health care professional (surgical oncologist, or medical oncologist). Data collection is done via PROFILES. Chapter 12 describes the use of PROFILES in more detail.

Patients are asked to complete the following questionnaires once. More information about these questionnaires can be found in Appendix 1.

Questionnaire A: Baseline questionnaire, version 1.0 (21 questions)

Questionnaire B: Health care utilization, version 1.0 (7 questions)

Questionnaire C: Decision-making, version 1.0 (6 questions)

Questionnaire D: EORTC QLQ-C30, version 3.0 (30 questions)

Questionnaire E: DTF-QoL, version 1.0 (102 questions)

Questionnaire F: EQ-5D-5L, version 1.0 (7 questions)

Clinical characteristics (8.1.3) will be collected from the medical records.

Patients are assured that non-participation has no consequences for their treatment or follow-up care. If the patient does not have access to internet, or prefers written rather than digital communication, (s)he will receive a paper version of the questionnaire package. The informed consent form and questionnaires are then sent by post.

The questionnaire will be available at [www.profielstudie.nl](http://www.profielstudie.nl) for a total of three months. Patients only have to fill out the questionnaire once but are able to stop at any given time point and are able to continue the questionnaire at any given time point. In case only a part of the questionnaire is filled out, the patient will receive a reminder (via PROFILES) to fill out the remaining questionnaire. Patients will receive a reminder 4 weeks after the first invitation.

Patients will be made aware of the fact that additional data will be obtained from their electronic patients files in the patient information file and will sign informed consent for this on the informed consent form.

## **8.4 Withdrawal of individual subjects**

Subjects can leave the study at any time for any reason if they wish to do so without any consequences.

### **8.4.1 Specific criteria for withdrawal (if applicable)**

Not applicable, as this is not an interventional study

**8.5 Replacement of individual subjects after withdrawal**

Not applicable, as this is not an interventional study.

**8.6 Follow-up of subjects withdrawn from treatment**

Not applicable, as this is not an interventional study.

**8.7 Premature termination of the study**

Not applicable, as this is not an interventional study.

**9. SAFETY REPORTING**

As this is not an interventional study and patients are not subjected to treatment in this study, this does not apply.

**9.1 Temporary halt for reasons of subject safety**

As patients are not subjected to treatment in this study, this does not apply.

**9.2 AEs, SAEs and SUSARs**

**9.2.1 Adverse events (AEs)**

As patients are not subjected to treatment in this study, this does not apply.

**9.2.2 Serious adverse events (SAEs)**

As patients are not subjected to treatment in this study, this does not apply.

**9.2.3 Suspected unexpected serious adverse reactions (SUSARs)**

As patients are not subjected to treatment in this study and the study does not involve an investigational medicinal product, this does not apply.

**9.3 Annual safety report**

As patients are not subjected to treatment in this study and the study does not involve an investigational medicinal product, this does not apply.

**9.4 Follow-up of adverse events**

As patients are not subjected to treatment in this study and the study does not involve an investigational medicinal product, this does not apply.

**9.5 [Data Safety Monitoring Board (DSMB) / Safety Committee]**

As patients are not subjected to treatment in this study and the study does not involve an investigational nor a non-investigational medicinal product, this does not apply. No DSMB will be installed for this study. No safety measures are involved since there are no risks involved in administering questionnaires to the patients.

**10. STATISTICAL ANALYSIS**

Rstudio (RStudio, version 1.0.153, Boston, MA, USA) and SPSS Statistics (version 24, IBM, Armonk, New York, USA) will be used for the statistical analysis.

The following questionnaires are descriptive outcomes and will be expressed as numbers and corresponding percentages:

Questionnaire A: Baseline questionnaire, version 1.0

Questionnaire B: Health care utilization, version 1.0

Questionnaire C: Decision-making, version 1.0

Questionnaire E: DTF-QoL, version 1.0

More information about these questionnaires can be found in Appendix 1.

### **10.1 Primary study parameter(s)**

The scores for each item of the DTF-QoL will be calculated using a Likert scale from 1-4. The scores of each item will be calculated as mean  $\pm$  SD, or as median (IQR). These scores (median or mean) will be reported per item.

The scores of the EORTC-QLQ30 (version .3.0) will be calculated using a Likert scale from 1-4. The scoring manual of the EORTC will be followed. After linear transformation, all scales and single item measures range in score from 0-100^14. Scores for each scale will be reported as mean (SD), or as median (IQR). The EORTC QLQ-C30 summary score will be calculated using the mean scores of the function scales and the reversed mean scores of the symptom scales and represented as the mean of the combined 13 QLQ-C30 scale scores (financial impact and global health status excluded).

Each of the five dimensions of the EQ-5D-5L (version 1.0) can be divided into five levels of perceived problem (1-5). Health states can be converted into single index values. The outcomes will be reported as frequency (proportion) of reported problems for each level and for each dimension. The Visual Analogue Scale (VAS) data will be presented as a mean value (SD). In case of skewed data, median values and IQR will be used.

### **10.2 Secondary study parameter(s)**

Using the baseline values (reported in the baseline questionnaire) for age and sex, patients will be matched, using a 1:10 nearest-neighbour match method, with the general population based on age, and sex using Rstudio (RStudio, version 1.0.153, Boston, MA, package MatchIt).

Differences in scores (of the EORTC QLQ-C30 scales between groups will be tested for their significance using the Mann-Whitney U test or the t-test, depending on the distribution. SPSS Statistics (IBM, Armonk, New York, USA, version 24) will be used for these tests. A two-sided  $p < 0.05$  will be considered statistically significant.

The outcomes of the health care utilization and the decision making questionnaire will be reported in numbers and corresponding percentages per answer option.

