#### **4.2 Inclusion criteria**

In order to be eligible to participate in this study, a subject must meet all of the following criteria:

- Patients, aged  $\geq 18$  years
- Patients with histopathological proven DTF, regardless of disease stage or treatment.
- Patients diagnosed between January 1990 and October 2019, with a visit to the hospital for their DTF (between October 2014 and October 2019)
- Patients with sufficient Dutch language skills
- Patients competent to complete a questionnaire
- Patients with a written informed consent

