#### **4.4 Sample size calculation**

The incidence of DTF is 5.4 patients per million per year. However, a sample size calculation is challenging due to rarity of the disease and lack of published data regarding this subject. In our previous study, the response rate of the Dutch patients was 41.5%. The Erasmus MC pathology database from 1990 until 2019 contains roughly 250 patients. Since we are a tertiary academic centre, about one third of these patients are pathology consultations from other centres. A small fraction of the remaining patients will be excluded because they are younger than 18 years old (about 5%) and because their desmoid tumour is part of the genetic syndrome Familial Adenomatous Polyposis (FAP) (about 5%). Because of the high incidence of malignant colorectal tumours in FAP patients, these patients might experience different HRQoL problems compared to patients with "sporadic" DTF. Currently, there are about 80 patients who are under follow-up at our institution. With the participation of two other centres with similar patient numbers we hope to approach a total of 250 patients. Based on the previous response rate we expect to obtain data from 100 DTF patients.

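### Section 10.2 leaves open which test compares patients with the norm; at 1:10, a pooled t-test or Mann-Whitney holds 5% only if the two groups have similar spread

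*Combined protocol and SAP*

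**What the plan says.** Secondary objective 1 compares the HRQoL of patients with that of the general population. Section 10.2 matches each patient to norm subjects "using a 1:10 nearest-neighbour match method", on age and sex, and tests differences in QLQ-C30 scale scores "using the Mann-Whitney U test or the t-test, depending on the distribution". The threshold is explicit: "A two-sided $p < 0.05$ will be considered statistically significant".

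Four things are left open: the criterion for judging the distribution; whether it is judged in patients, norm subjects or both; whether the choice is made once or for each scale; and whether the t-test is the pooled or the unequal-variance form. Section 8.1.2 has the same ambiguity, since it allows either medians or means to be compared.

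The group sizes follow from section 4.4: "Based on the previous response rate we expect to obtain data from 100 DTF patients". The patient group is broad by design (section 4.2): "Patients with histopathological proven DTF, regardless of disease stage or treatment". No SD is given for patients or for the norm.

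**The concern.** The t-test compares means and Mann-Whitney compares ranks. Until the data are seen, the plan does not fix which quantity is being compared.

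The 1:10 ratio makes the missing t-test version matter. With 100 patients and 1,000 norm subjects, the pooled variance takes 999/1,098 = 91% of its weight from the norm group. Yet with equal spread, 0.010 of the 0.011 in the variance of the mean difference (also 91%) comes from the patients. If patients are more spread out than the norm, the pooled standard error is too small. If they are less spread out, it is too large. Patients at every disease stage and after any treatment could plausibly have a wider spread, but the documents do not show that they do. At stake is the calibration of the p-values for objective 1.

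**Working it through.** **1. Group sizes (section 4.4).** The plan expects 100 patients. Three centres of about 80 give 240, and 240 × 0.415 = 99.6, which reproduces that figure. Using the stated 250 approached, 250 × 0.415 = 103.75. At 1:10 the comparison is therefore about 100 against 1,000. Using 104 against 1,040 leaves the pooled t-test results below unchanged to one decimal.

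**2. Assumption.** Let r be the patient SD divided by the norm SD. The documents do not give it, so a range is shown.

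**3. Pooled t-test, matching ignored, equal means.** With the norm SD set to 1:

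- pooled variance s² = (99r² + 999)/1,098
- variance the test uses: s² × (1/100 + 1/1,000) = 0.011 s²
- true variance: r²/100 + 1/1,000
- true size = 2 × [1 − Φ(1.96 × √(0.011 s² / true variance))]

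At r = 1.25, s² = 1.0507. The test uses 0.01156 and the true variance is 0.016625. The SE ratio is 0.834, 1.96 × 0.834 = 1.634, and the size is 10.2%. At r = 1.5 the SE ratio is 0.722 and the size 15.7%. At r = 0.8 the SE ratio is 1.199 and the size 1.9%.

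**4. All tests, 100 against 1,000, equal means, nominal 5%.** The pooled t column is from the formula. The others are simulated on normal scores with 10,000 runs (Monte Carlo SE about 0.2 to 0.3 points).

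| r | Pooled t | Mann-Whitney | Unequal-variance t |
|---|---|---|---|
| 0.8 | 1.9% | not run | not run |
| 1.0 | 5.0% | 5.4% | 5.6% |
| 1.1 | 7.0% | 5.9% | 4.7% |
| 1.25 | 10.2% | 7.8% | 5.2% |
| 1.5 | 15.7% | 9.6% | 4.9% |

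At 100 against 100, the pooled t-test and Mann-Whitney stay between 5.1% and 5.5% for r from 1.25 to 2.0. The exposure therefore comes from the unequal group sizes.

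**5. Effect of the matching.** If age and sex explain part of the score variance and the test ignores the matched sets, all three sizes fall. At r = 1.25:

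| Variance explained (assumed) | Pooled t | Mann-Whitney | Unequal-variance t |
|---|---|---|---|
| 0% | 10.1% | 7.2% | 5.0% |
| 10% | 8.6% | 6.4% | 3.8% |
| 20% | 7.5% | 5.5% | 3.5% |

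**6. Skewed scores.** The unequal-variance t-test stays at 5.2% to 5.7% on the bounded 0–100 scores tried, and reaches about 6% at worst under strong skew. A constructed four-level item shows why the choice between means and ranks matters. Both groups have mean 21.7, with SD 33.8 in patients and 28.4 in the norm (ratio 1.19). The unequal-variance t-test rejects in 5.5% of runs, the pooled t-test in 8.8% and Mann-Whitney in 21%. Brunner-Munzel, a rank test that allows unequal spread, rejects in 19%. Most of the Mann-Whitney excess is thus a real difference in ranking, not a variance error.

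**7. The selection step.** Choosing by a Shapiro-Wilk pre-test at r = 1.25 on normal scores gives 10.4%, practically the same as the pooled t-test alone.

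**The case against.** The strongest reply is that the key input is assumed. No SD appears in the documents, a mixed case-load does not prove wider scores, and a general population also mixes well and ill people. At r = 1.0 nothing is wrong, at 1.1 the excess is small, and at 0.8 the pooled test is conservative. All of this stands, so the figures are conditional and can err in either direction.

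Four stronger readings are tempting, and the documents do not support them:

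- **The planned t-test fails.** The plan does not say it is pooled. If the unequal-variance form was meant, the t-test excess disappears.
- **Choosing the test from the data inflates the error.** No figure here isolates harm from the selection step. Step 7 shows none on normal scores.
- **Mann-Whitney is invalid.** It is valid for identical distributions. The 8% and 10% count as errors only if it is read as a test of equal location, a hypothesis that section 10.2 does not state.
- **10% is the expected error rate.** That figure ignores the age and sex matching, which can lower it.

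It is also fair to say that preferring means for every scale, including four-level single items, is a choice of target quantity, and that section 1 calls the study exploratory. Neither removes the point. The plan declares significance at 5%, and a method that holds that level without an equal-spread assumption is available at almost no cost.

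**Conclusion.** The concern holds in conditional form. The test for objective 1 is left to the observed distribution, with no criterion and no t-test version, at an allocation where the version matters. If the pooled form is used and matching is ignored, the true size at nominal 5% runs from 1.9% to 15.7% over SD ratios 0.8 to 1.5. At 1.25 it is 10.2%, or about 7.5% to 8.6% if age and sex explain 20% to 10% of the variance. Mann-Whitney, read as a location test on symmetric scores, rejects about 8% at 1.25 and 10% at 1.5. The unequal-variance t-test stays near 5%.

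These figures assume that 1:10 is achieved with 100 patients; a smaller ratio would weaken the effect. A reader might infer that the study's main results are compromised. They are not: the primary analysis in section 10.1 is descriptive and this comparison is secondary. The consequence is miscalibrated p-values on scales where the spreads differ.

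**What to change.** In section 10.2, delete the clause that lets the distribution choose the test, and name one primary analysis for all QLQ-C30 scales. Suggested wording: *For each scale, the difference in mean score between patients and matched norm subjects will be estimated with an unequal-variance (Welch) or heteroscedasticity-robust standard error, taking account of the matched sets, and reported with a 95% confidence interval. A rank test will be reported as a sensitivity analysis.* Change section 8.1.2 to match, so that it no longer leaves the choice between medians and means open. Medians can still be shown descriptively.

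Respecting the matched sets is preferable because a plain Welch test becomes somewhat conservative when age and sex predict the score (3.5% to 3.8% in step 5). If the sets do not overlap, one simple version subtracts the mean of each patient's ten controls from the patient's score and applies a one-sample t-test to the roughly 100 differences. With no correlation within sets, the variance of their mean is (r² + 1/10)/100 = r²/100 + 1/1,000, the true variance in step 3, with no equal-spread assumption.

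The cost is a short edit in two sections and keeping the matched-set identifier. Both packages named in section 10 provide the unequal-variance test. The downside is a negligible loss of precision if the variances are equal, and a size of about 6% at worst on strongly skewed scales.
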